## 4.9. Interim Analyses

### 4.9.1. Interim Analysis for Regulatory Submission

As the study will be still ongoing at the time of regulatory submission, interim analyses will be performed in order to provide open-label safety and efficacy data in an interim Clinical Study Report (CSR) to inform the risk-benefit assessment of GSK3511294 in asthma with an eosinophilic phenotype..

At interim a ‘cut’ will be made in the data, where any data collected beyond a prespecified cut-off date will not be included within the datasets to be reported. The interim analysis will include the analyses specified in this analysis plan. The details of the outputs are in the OPS.

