9.2. Sample Size Determination

There is no sample size calculation for this study since this is an estimation study with the primary aim to estimate long-term safety outcomes. The sample size will be determined by the number of available participants who were randomised into Study 206713 and Study 213744 and are eligible for the current study based on inclusion and exclusion criteria.

This study is an extension of Study 206713 and Study 213744. Participants must have completed the study intervention during Study 206713 or 213744 prior to entering this study. The maximum number of participants who are potentially eligible to take part in this study is approximately 750. Assuming 15% drop out rate, 637 will be enrolled into this open label safety study.

The primary endpoints are incidence of AE/SAE and incidence of immunogenicity as measured by the presence of ADA/NAb to GSK3511294. [Table 2](#) gives the probability of observing various numbers of events over an averaged on-treatment observation period, e.g., AE, for different anticipated population risks given a sample size of 637. For example, for a risk of an AE of 1/1000, we would have approximately 50% chance of observing at least one AE over an averaged on-treatment observation time period. Also, for a risk of 1/10,000, would have 6.5% chance of seeing at least one AE over an averaged on-treatment observation time period

Table 2 Probabilities of observing a given number of adverse events or more (k)

| k | Risk of an Event | | | | | |
|----|------------------|--------|--------|---------|---------|---------|
| | 0.0200 | 0.0100 | 0.0050 | 0.0020 | 0.0010 | 0.0001 |
| 1 | >0.9999 | 0.9983 | 0.9590 | 0.7206 | 0.4713 | 0.0617 |
| 2 | >0.9999 | 0.9877 | 0.8276 | 0.3640 | 0.1342 | 0.0019 |
| 3 | 0.9997 | 0.9534 | 0.6176 | 0.1368 | 0.0269 | <0.0001 |
| 4 | 0.9988 | 0.8801 | 0.3942 | 0.0404 | 0.0041 | |
| 5 | 0.9958 | 0.7628 | 0.2164 | 0.0098 | 0.0005 | |
| 6 | 0.9879 | 0.6128 | 0.1032 | 0.0020 | 0.0001 | |
| 7 | 0.9711 | 0.4532 | 0.0433 | 0.0004 | <0.0001 | |
| 8 | 0.9400 | 0.3079 | 0.0162 | 0.0001 | | |
| 9 | 0.8901 | 0.1923 | 0.0054 | <0.0001 | | |
| 10 | 0.8190 | 0.1107 | 0.0016 | | | |

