9.5. Interim Analysis

As the study will be still ongoing at the time of regulatory submission, interim analyses will be performed in order to provide open-label safety and efficacy data in an interim Clinical Study Report (CSR) to inform the risk-benefit assessment of GSK3511294 in severe asthma. The Statistical Analysis Plan will describe the planned interim analyses in greater detail.

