### 1.1.2. Estimand

The following two attributes apply to all estimands:

- Population: Adult and adolescent participants with severe asthma with an eosinophilic phenotype on top of existing asthma therapy
- Treatment: GSK3511294 100 mg (SC) given every 26 weeks on top of SoC.
  - ✓ open-label GSK3511294 + SoC and on GSK3511294 + SoC in previous study
  - ✓ open-label GSK3511294 + SoC and on placebo + SoC in previous study

Estimand		
Endpoint	Intercurrent Event Strategy	Population Level Summary Measure
Primary objective (Safety): To describe the long-term safety profile of GSK3511294 100 mg (SC) every 26 weeks in participants with severe asthma with an eosinophilic phenotype on top of existing asthma therapy over a 12 month open label extension phase		
a) Incidence of AEs/SAEs over 52 weeks	
 
Study intervention discontinuation due to reasons unrelated to the
 
	a) Number and percentage of participants with any

[figure not shown]
Estimand		
b) Incidence of immunogenicity as measured by the presence of ADA/NAb to GSK3511294 over 52 weeks	
COVID 19 pandemic: while on-treatment strategy i.e. using data up until 26 weeks after last dose of GSK3511294. This strategy is to summarise the events while the participants are exposed to the treatment.
 
 
• Study intervention discontinuation due to reasons related to the COVID-19 pandemic: while on-treatment strategy i.e. using data up until 26 weeks after last dose of GSK3511294
 
• Change in maintenance therapy or use of prohibited medications: CCI [REDACTED] [REDACTED] [REDACTED] [REDACTED]
 
	
AEs and incidence rate of AEs over 52 weeks
 
b) Number and percentage of participants with incidence of immunogenicity as measured by the presence of ADA/NAb to GSK3511294 and mean titre results over 52 weeks

Secondary Objective (Efficacy): To evaluate the effects of long-term dosing of GSK3511294 100 mg (SC) every 26 weeks on a range of clinical markers of asthma control and additional efficacy assessments on top of existing asthma therapy over a 12-month open label extension phase		

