## 2. STATISTICAL HYPOTHESES

Because the study has a single treatment arm, statistical analyses of treatment effect will not be performed. Therefore, no hypotheses have been defined for this study.

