## 3. ANALYSIS SETS

Analysis Set	Definition / Criteria	Analyses Evaluated
Screened	All participants who were screened for eligibility.	
 
• Study Population
 

Enrolled	
All participants who entered the study (who received study intervention or underwent a post screening study procedure).
 
Note screening failures and participants screened but never enrolled into the study (Met eligibility but not needed) are excluded from the Enrolled analysis set as they did not enter the study.
	
 
• Study Population
 

Safety	All participants who receive at least one dose of open-label GSK3511294 excluding participants from sites 250190, 250085 and 250523	
 
• Study Population
 
• Safety
 
• Efficacy
 
• Immunogenicity
 
• PD
 

Safety-Japan	All participants in the Safety population who are enrolled from Japan and with Japanese heritage only	
 
• Study Population
 
• Safety
 
• Efficacy
 
• Immunogenicity
 
• PD
 

Safety-Non-Japan	All participants in the Safety population who are not in Safety-Japan analysis set	
 
• PD
 

Safety-Modified	All participants in the Safety population plus enrolled participants from sites 250190, 250085 and 250523 who received at least one dose of study intervention.	
 
• Key Safety
 

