## 4.6. Immunogenicity Analysis

For the immunogenicity assessment, two types of anti-drug antibody (ADA) assays will be performed, a binding antibody assay and a neutralizing antibody assay (NAb).

[figure not shown]
For the binding assay, there will be a three-tiered analysis: screening, confirmation and titration. The screening assay produces a result of positive or negative relative to a screening cut point. Positive samples continue with the confirmation assay, which also produces a result of positive or negative relative to a confirmation cut point. For positive confirmation samples, a titre value will also be obtained to quantify the degree of binding in a titration assay, and the sample will be tested with the neutralizing assay, which also reports results as positive or negative. A sample that is positive in the confirmation assay is considered positive for anti-GSK3511294 antibodies.

The following descriptive summaries will be presented by visit using Safety population

- Summary of binding antibody assay results: it will summarise the binding antibody confirmatory assay results at each visit. Summary will include categories for negative and positive results, sub-categories for transient positive and persistent positive (see note below), and available titre values (min, median and max). It will also summarise the highest post-baseline binding antibody confirmatory assay result obtained.
- Summary of neutralizing antibody assay results: it will summarise the neutralising antibody assay results for participants with a positive binding antibody confirmatory assay result. Neutralising antibody assay results will be categorised as positive or negative. It will also summarise the highest post-baseline neutralizing antibody assay result obtained.
- Summary of AE by highest post-baseline binding antibody confirmatory assay result

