#### 6.1.1. Participant Disposition

A summary of the number and percentage of participants who completed the study as well as those who prematurely withdrew from the study will be provided. Reasons for study withdrawal will be summarised. For those who have neither completed nor withdrawn, they will be categorized as on study intervention or in follow up.

A summary of study intervention status will be provided. This display will show the number and percentage of participants who have completed the scheduled study intervention, are ongoing with study intervention, or have discontinued study intervention prematurely, as well as primary reasons for discontinuation of study intervention.

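### Interim AE, SAE, AESI and cumulative ADA percentages use the whole Safety set with no follow-up rule, so they read low as 52-week incidences

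*SAP*

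**What the plan says.** The first primary endpoint in SAP 1.1.2 is "Incidence of AEs/SAEs over 52 weeks". The second, presence of ADA/NAb, has the same horizon, and so do the summary measures of both.

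Protocol 9.5 and SAP 4.9.1 plan an interim report for the regulatory risk-benefit assessment: "As the study will be still ongoing at the time of regulatory submission, interim analyses will be performed". Data beyond a prespecified cut-off date are removed, and "The interim analysis will include the analyses specified in this analysis plan". Neither document gives the cut-off date, the accrual pattern or a minimum follow-up.

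The default population (SAP 4.1.1) is the Safety set, defined in SAP 3 as "All participants who receive at least one dose of open-label GSK3511294", less participants from three named sites. There is no interim analysis set.

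For AEs, SAEs and AESIs, SAP 4.5.2 and 4.5.2.1 plan counts and percentages. For binding antibodies, SAP 4.6 plans results by visit and adds: "It will also summarise the highest post-baseline binding antibody confirmatory assay result obtained". NAb results are summarised among participants with a confirmed positive binding result.

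Ongoing participants are mentioned only for disposition, in SAP 6.1.1: "For those who have neither completed nor withdrawn, they will be categorized as on study intervention or in follow up".

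**The concern.** A percentage described as an incidence over 52 weeks needs a denominator of people who had 52 weeks in which the event could occur. At the interim, someone dosed a few weeks before the cut counts fully in the denominator and, unless an event has already happened, counts as event-free.

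The while-on-treatment strategy does not deal with this. It covers stopping study intervention, not administrative truncation at a data cut. SAP 4.5.2 has no time-to-event or other method that allows for censoring.

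The bias has one direction: it makes the product look safer and less immunogenic, in the report meant to inform the risk-benefit assessment.

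**Working it through.** **1. The plan's own figure.** Protocol 9.2 says that "The maximum number of participants who are potentially eligible to take part in this study is approximately 750" and assumes 15% drop-out: 750 × 0.85 = 637.5, given as 637. Table 2 gives the probability of at least one event at risk 0.001 as 0.4713. Check: 1 − (1 − 0.001)^637 = 0.4713. The figure reproduces, and it supposes that all 637 carry the full risk.

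**2. Will anyone be short of Week 52?** Participation lasts at most 56 weeks (Protocol 1.1). If the study is still running at submission, the last entrants are within about 56 weeks of their first dose, and the data cut comes no later than submission. Unless everyone still in the study has already passed Week 52 at the cut, some participants are short of it. How many cannot be derived.

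**3. Size for AE-type percentages.** Assumptions, none of them in the documents:
- a share f of the Safety set is short of Week 52;
- their follow-up is uniform over 0–52 weeks;
- the hazard is constant, λ = −ln(1 − P), where P is the true 52-week incidence.

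Expected interim percentage = (1 − f)·P + f·[1 − (1 − e^−λ)/λ].

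Example, P = 10%, f = 25%: λ = 0.1054, the bracket is 5.09%, and 0.75 × 10 + 0.25 × 5.09 = 8.77%.

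| True P | f = 10% | f = 25% | f = 50% |
|---|---|---|---|
| 70% | 67.2% | 63.0% | 55.9% |
| 50% | 47.8% | 44.5% | 38.9% |
| 10% | 9.5% | 8.8% | 7.5% |
| 5% | 4.8% | 4.4% | 3.8% |
| Relative loss | 4–5% | 10–12% | 20–25% |

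At a risk of 0.001 the effective risk at f = 50% is 0.00075, and the 0.4713 of step 1 becomes 1 − (1 − 0.00075)^637 = 0.380.

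**4. Cumulative ADA.** The schedule of activities has post-baseline samples at Weeks 12, 26, 40 and 52. With the same assumptions and P = 10%, positivity counts only once a sample has been taken. Mean detection among those short is [14 × 2.40% + 14 × 5.13% + 12 × 7.79%]/52 = 3.82%. A share 12/52 = 23% of them has no post-baseline sample. SAP 4.6 does not state the denominator, so both versions are shown.

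| Denominator | f = 10% | f = 25% | f = 50% |
|---|---|---|---|
| Whole Safety set | 9.4% | 8.5% | 6.9% |
| Those with a post-baseline sample | 9.6% | 9.0% | 7.8% |

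Limiting the denominator to sampled participants reduces the bias but does not remove it.

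**5. Would an incidence rate cure it?** SAP 4.5.1 takes exposure as final-dose date minus first-dose date plus 182 days, and states no truncation at the cut. Take the second dose at Week 26 and no discontinuation. Someone short of Week 26 is credited with 26 weeks, and someone between Weeks 26 and 52 with 52 weeks. The average credited is 39 weeks, against 26 weeks observed.

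Credited/observed = [52(1 − f) + 39f]/[52(1 − f) + 26f]:
- f = 10%: 50.70/49.40, subject-years 2.6% too high;
- f = 25%: 48.75/45.50, 7.1% too high;
- f = 50%: 45.50/39.00, 16.7% too high.

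A rate built on these subject-years would be low by about 2.6%, 6.7% and 14.3% (1 minus the inverse ratio).

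**The case against.** The study is descriptive ("no hypotheses have been defined for this study"), no decision rule depends on these percentages, and the final report is unaffected. Disposition tables will show how many participants are ongoing, so short follow-up would be visible. No AE table is titled as a 52-week table, and Protocol 9.2 speaks of risk over an average on-treatment period, so unequal observation was foreseen. Output details are left to the OPS, which is not available here and might settle denominators. All of this stands and limits the weight of the point. It does not remove it: the endpoints and summary measures carry the 52-week horizon, and the rule for who enters a primary-endpoint denominator belongs in the SAP.

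Several stronger readings are tempting but unsupported:
- **Severe dilution.** A reader might infer that a true 70% would be reported as about 42%. That needs the whole Safety set to be short of Week 52, as with uniform entry over 12 months and a cut on the day of the last entry. Nothing in the documents points to so early a cut.
- **Everyone dosed is in the denominator.** Three sites are outside the Safety set. Their AEs appear in the Safety-Modified overview and a listing (SAP 4.5.4).
- **All antibody results are diluted.** By-visit ADA need not be, if the denominator is those with a result at that visit. NAb among ADA-positive participants is not diluted in the same way.
- **No exposure-based measure was planned.** SAP 1.1.2 and Protocol 9.4.2 do name an AE incidence rate. The weakness is that SAP 4.5.2 does not carry it through and the available exposure formula would bias it.
- **The figures cannot be compared with the parent studies.** Those studies' analysis plans are not available here, and SAP 2.1 plans no treatment comparison in this study.

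**Conclusion.** The point holds for the interim AE, SAE and AESI percentages and for the cumulative highest post-baseline ADA percentage. As 52-week incidences they are biased low whenever Safety-set participants are less than 52 weeks from first dose at the cut, and the plan makes it very likely that some will be.

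The direction is certain; the size is not. The 4–5%, 10–12% and 20–25% relative losses for AE-type percentages rest on assumed shares of 10%, 25% and 50%, uniform follow-up and a constant hazard. Earlier onset of first events would shrink them, and a late cut takes them close to zero. The ADA figures also assume that nobody is positive at the start, although some participants had already received the drug in the parent studies.

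The change should be made before the interim outputs are fixed. It corrects a bias at little cost, but it does not put the study's final conclusions in doubt.

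**What to change.** Keep the all-Safety-set interim tables, title them 'to data cut-off', and add to SAP 4.9.1:

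(a) 52-week percentages for AEs, SAEs, AESIs and cumulative ADA are also shown for participants whose first open-label dose was at least 364 days before the cut-off date, whether or not they discontinued or withdrew. Selecting on first-dose date alone avoids completer bias.

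(b) AE and SAE incidence rates are given for all Safety-set participants, with exposure ending at the earlier of last dose + 182 days and the cut-off date.

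(c) The number of participants short of Week 52 at the cut is stated.

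The cost is a short SAP addition, one date-based flag, one exposure variable and a few extra tables. The 52-week percentages will rest on fewer participants, possibly very few if the cut is early; in that case (b) becomes the main interim measure. Because visits have a ±7-day window, a few participants just past 364 days may still lack their Week 52 ADA sample, so the number with that sample should be shown beside the ADA percentage.

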### 4.9.2. IDMC

IDMC will periodically review safety data from the study in accordance with the IDMC Charter.

The IDMC will review all safety data, including AEs and serious adverse events (SAEs) and adverse events of special interest (AESI), laboratory parameters, including haematological and clinical chemistry parameters and ECG assessments from the three studies for identification of any potential safety signals.

Data from Study 212895 is being provided for information to the IDMC as potential supporting data for the overall assessment of safety for use of GSK3511294 in the 206713, 213744 and 206785 study population. The IDMC will not issue recommendations for the conduct of Study 212895.

## 4.10. Changes to Protocol Defined Analyses

None.

## **5. SAMPLE SIZE DETERMINATION**

There is no sample size calculation for this study since this is an estimation study with the primary aim to estimate long-term safety outcomes. The sample size will be determined by the number of available participants who were randomised into Study 206713 and Study 213744 and are eligible for the current study based on inclusion and exclusion criteria.

## 6. SUPPORTING DOCUMENTATION

### 6.1. Appendix 1 Study Population Analyses

Unless otherwise specified, the study population analyses will be based on the Safety Analysis Set. A summary of the number of participants in each of the participant level analysis set will be provided.

In this multicentre global study, enrolment will be presented by country and site.

All summaries will be presented overall and by previous treatment groups.

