9.3. Analysis Sets

| Analysis Set | Description |
|--------------|--|
| Screened | All participants who were screened for eligibility |
| Enrolled | All participants who entered the study (who received study intervention or underwent a post screening study procedure). Note screening failures and participants screened but never enrolled into the study (Met eligibility but not needed) are excluded from the Enrolled analysis set as they did not enter the study. |
| Safety | All participants who receive at least one dose of open-label GSK3511294. |

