## Version history

SAP Version	Approval Date	Protocol Version (Date) on which SAP is Based	Change	Rationale
01	23 Feb 2022	01(30-JUL-2021)	Not Applicable	Original version
02	23 Jul 2024	01(30-JUL-2021)	
Update to analysis sets in Section 3. Inclusion of additional analyses on the Safety-modified analysis set.
 
Update categories for region in Section 4.1.3
 
Additional sentence added at end of 4.5.2
 
Removal of a immunogenicity data summary in Section 4.6
 
Update in Section 4.7
	
Minor modification to Japan subset and update to account for site with GCP non-compliance.
 
To be consistent with study 206713 and 213744.
 
Reference to additional AE display for broad SMQ 'Torsade de pointes/QT Prolongation'
 
Not required for this extension study
 
Update of imputation for limit of quantification

03		01(30-JUL-2021)	Adding appendix 3	Per GSK new guidance adding eCOA Compliance

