## 4. STATISTICAL ANALYSES

### 4.1. General Considerations

#### 4.1.1. General Methodology

The Safety Analysis Set will be used for all Study Population, Efficacy, Safety, Immunogenicity and PD analyses, unless otherwise stated. The Output and Programming Specification (OPS) document will provide more details.

Confidence intervals will use 95% confidence levels unless otherwise specified.

Unless otherwise specified, continuous data will be summarised using descriptive statistics: n, mean, standard deviation (std), median, minimum and maximum. Categorical data will be summarised as the number and percentage of participants in each category.

A subset of Study Population, Efficacy, Safety, Immunogenicity and PD outputs will be produced for Safety-Japan (and Safety-Non-Japan) analysis sets. A list of these outputs will be included in the OPS.

Additional output(s) will be produced for Safety-Modified analysis set, see OPS for details.

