### **6.1.3. Protocol Deviations**

Important protocol deviations will be summarised.

Protocol deviations will be tracked by the study team throughout the conduct of the study. These protocol deviations will be reviewed to identify those considered as important as follows:

- Data will be reviewed prior to freezing the database to ensure all important deviations are captured and categorised in the protocol deviations dataset.
- This dataset will be the basis for the summaries of important protocol deviations.

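### Disposition, study intervention status and important protocol deviations default to a Safety set that excludes three sites, and no SAP-named output fills the gap

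*SAP*

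**What the plan says.** Two SAP sections set the same default. Section 6.1 (Appendix 1) says: "Unless otherwise specified, the study population analyses will be based on the Safety Analysis Set". Section 4.1.1 says: "The Safety Analysis Set will be used for all Study Population, Efficacy, Safety, Immunogenicity and PD analyses, unless otherwise stated".

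SAP section 3 defines the Safety set as: "All participants who receive at least one dose of open-label GSK3511294 excluding participants from sites 250190, 250085 and 250523". Protocol 9.3 defines it as: "All participants who receive at least one dose of open-label GSK3511294", with no site removed. The SAP version history attributes the version 02 change to the analysis sets in part to an "update to account for site with GCP non-compliance".

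Section 6.1.1 describes the disposition and study intervention status summaries without naming a set. Section 6.1.3 says "Important protocol deviations will be summarised", also without naming one. The only place in Appendix 1 that departs from the default is 6.1.2, which puts the age categories on the Enrolled set.

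The Safety-Modified set is defined as: "All participants in the Safety population plus enrolled participants from sites 250190, 250085 and 250523 who received at least one dose of study intervention". Section 3 assigns it to key safety. Section 4.5.4 names two outputs for it: an overview of adverse events, and a listing of adverse events from the three sites. SAP 4.10 reports no changes to protocol-defined analyses.

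**The concern.** Disposition and deviation tables are where a reader judges how a trial was conducted and how complete its follow-up was. Unreliable data from a site may justify leaving that site out of efficacy or safety estimates. That reasoning does not extend to the tables that report conduct, where such sites are most relevant.

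The study is single-arm and descriptive, with no hypotheses, so its credibility rests largely on these tables. Discontinuation of study intervention is also a named intercurrent event in the primary estimand, and the intervention status summary is where its frequency and reasons appear.

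The effect looks like a by-product rather than a decision. The version history records the change to section 3 but no change to 6.1. Under the protocol's Safety definition, the default in 6.1 would have kept all treated participants in these tables.

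**Working it through.** The plan states no figure to reproduce. The check is which set governs each output.

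**Set logic**

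| Step | Source | Result |
|---|---|---|
| Default for study population outputs | SAP 6.1 and 4.1.1 | Safety set |
| Members of the Safety set | SAP 3 | Treated participants, minus three sites |
| Override for disposition or intervention status | SAP 6.1.1 | None |
| Override for important deviations | SAP 6.1.3 | None |
| Override elsewhere in Appendix 1 | SAP 6.1.2 | Age categories only, on Enrolled |
| Outputs named for Safety-Modified | SAP 4.5.4 | AE overview and AE listing only |

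By definition, Safety-Modified minus Safety equals the treated participants at the three sites. These participants are absent from the three summaries. Enrolled minus Safety is that group plus anyone enrolled but never dosed, at any site. The undosed group should be small, because the first dose is given at Visit 1 and the Enrolled set excludes screen failures.

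The COVID-19 summaries of disposition, intervention status and deviations in SAP 4.5.2.3 inherit the same gap, because section 4.5 also defaults to the Safety set.

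**Illustration of size**

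The number treated at the three sites is not given. Assume n = 5, 15 or 30 out of 637. The 637 is the planning figure in protocol 9.2 (750 × 0.85 = 637.5, taken as 637), used here as if it covered everyone treated. Assume also that 15% of participants at the other sites have an important deviation.

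- Share omitted: n/637.
- Percentage reported on the Safety set: 15.0%.
- Percentage with the three sites included, if everyone there has a deviation: (0.15 × (637 − n) + n)/637.
- The same, if nobody there has one: 0.15 × (637 − n)/637.

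| n | Share omitted | All deviate | None deviate |
|---|---|---|---|
| 5 | 0.8% | (94.8 + 5)/637 = 15.7% | 94.8/637 = 14.9% |
| 15 | 2.4% | (93.3 + 15)/637 = 17.0% | 93.3/637 = 14.6% |
| 30 | 4.7% | (91.05 + 30)/637 = 19.0% | 91.05/637 = 14.3% |

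The two right-hand columns are the limits for each assumed n. If the three sites had the same rate as the rest, the figure would stay at 15.0%.

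**The case against.** Several points on the other side stand.

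- **The exclusion will be visible.** Section 6.1 requires a count of participants in each analysis set, and enrolment by country and site. These show that people were left out, but not how they left the study or what deviations occurred.
- **AE-related discontinuations are covered.** The overview described in SAP 4.5.2 counts AEs leading to discontinuation of study intervention or withdrawal from the study, and fatal SAEs. Section 4.5.4 repeats an AE overview with the three sites included. What remains missing is completion status, withdrawals for other reasons, and deviations.
- **There are other reporting routes.** Protocol 10.1.7 requires departures from quality tolerance limits to be summarised in the study report. Nothing in SAP 6.1.3 removes sites from the deviations dataset itself. Neither point changes the set on which the deviation summary is tabulated.
- **The output specification may settle it.** SAP 4.1.1 defers further Safety-Modified outputs to that document, which was not available, and section 3 lists Enrolled as usable for study population analyses. The point is therefore about the SAP text. A listed permitted use does not override a stated default, and the base for these tables belongs in the SAP.
- **The root cause lies elsewhere.** Restoring the protocol's Safety definition would return every treated participant to these tables with no edit to 6.1. The present point matters if the narrowed set is kept.

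A reader might also infer that these sites had the worst conduct, or were removed for misconduct, so that the tables are biased in a favourable direction. The documents do not support this. The version history mentions GCP non-compliance at a site, in the singular, while three sites are excluded. It does not describe the problem, rank sites or tie the reason to each one. For disposition even the direction is open: if most of these participants completed, leaving them out makes completion look worse.

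**Conclusion.** The point holds as a matter of the SAP's own rules. Followed as written, they leave the treated participants at three sites out of the disposition, study intervention status and important deviation summaries, and no output named in the SAP replaces what is lost. Whether the sites should be excluded from efficacy or safety estimates is a separate question, on which this point takes no position.

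Neither the size nor the direction of the effect can be established from the documents. Understated deviations are plausible, given the stated reason for the update, but not demonstrated. The range 15.7% to 19.0% should not be read as corrected percentages. It is the upper end of a scenario in which the number at the sites, the 15% elsewhere and the 100% at the sites are all assumed. The change is worth making because the omission is certain from the text and cheap to remove, not because a large bias has been shown.

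**What to change.** In SAP 6.1.1 and 6.1.3, state that disposition, study intervention status and important protocol deviations are summarised on the Enrolled Analysis Set, with sites 250190, 250085 and 250523 identifiable in the display. The Safety-set version can be kept as an optional secondary display. Name the set for the matching COVID-19 summaries in 4.5.2.3 in the same way.

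In SAP 4.10, record that the Safety set is narrower than in protocol 9.3, and give the reason for each of the three sites.

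The cost is a few lines of SAP text and two or three tables re-run on a set already defined, plus the COVID-19 summaries if they are included. No new data are needed. The percentages may become slightly less favourable.
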